Three main metrics will be measured during the pilot study: *Percentage of Correctly Transcribed Words Using ASR, Articulation Accuracy, and Mean Length of Utterance (MLU)*. These metrics will show whether there has been improvement in the participant’s functional language abilities, and oral motor coordination skills. They will be

analyzed by several trained staff members who will observe each recorded and monitored session.

Subject Selection

Recruiting: Subjects will be recruited by contacting (e.g. email or telephone) teachers and professionals (e.g. speech-language pathologists and behaviorists) who work with children with autism, aged 4 to 8. The research team will reach out to school administrators, teachers, and specialists through the iTherapy network of contacts to recruit eligible K-2 students diagnosed with ASD and their teacher or specialist. The VR-based VAST platform is designed for use with early elementary school-aged students (grades K-2). In order to conduct the intervention and gather data that would be useful for further development of the product, the research study must include early elementary school students.

In order to recruit enough children within the study's target population and to encourage retention, the study team will use online advertising via social media and other platforms (e.g. Craigslist) to reach participants. All participants will be given an Apple device (iPhone 6 for VR or refurbished iPad mini for 2D) for participating in the study and a free download of InnerVoice (valued at \$99.99), an iOS AI-powered communication app that uses video self-modeling, designed and sold by iTherapy.

Number of participants: 6

Inclusion/Exclusion criteria: All participants will be recruited via campaigns posted on social media and/or other platforms: parents/guardians will be provided consent forms and all information regarding inclusion/exclusion criteria.

Children **under the age of 18** will be recruited and all protections mandated by NIH policy afforded to them.

In order to protect participants and their families from COVID-19 exposure, participants will undergo Aim 3's procedures within their homes: the subjects' data will be collected using a HIPAA-compliant telehealth video-streaming platform. The goal of this

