procedure is to minimize any potential exposure to infection as a result of participating in this study. The study's team will follow CDC-recommended cleaning and disinfection guidelines to ship and retrieve the prototype VR headset (that is, the bone-conduction headphones along with the goggles sans the iPhones, which the participants can keep as part of participating in the study).

The proposed study will not discriminate based on gender, sexual orientation or race. Participants will be recruited from a pool of children at participating clinics and educational facilities independent of the above-mentioned aspects. There are no exclusion criteria based on gender, sexual orientation, or race.

Because data prior studies strongly support no significant differences of clinical or public health importance in intervention effect between subgroups, then sex/gender and/or race/ethnicity will not be recorded as subject selection criteria.

Children with a medically documented history of seizure disorder will be excluded from the study. According to Carnegie Mellon University Entertainment Technology Center (2019), individuals with a history of seizure disorder should avoid using virtual reality media.

Study procedures / research method

Due to health and safety concerns associated with the COVID-19 pandemic, the feasibility procedures will be conducted through a HIPAA-compliant telehealth platform. The subjects' caregivers or parents will help measure the impact of two pieces of technology: the 3D VR-integrated headset with bone-conduction and the 2D tablet-based application.

In order to prevent the spread of pathogens among large groups of subjects, the number of participants has been reduced from 30 to 10. Ten ASD students between the ages of 4 and 8 will be recruited to participate in a 14-sessions-long study that will utilize the integrated VAST application. The subjects will each receive a different piece of technology: one group of five will receive a 3D VR-integrated VAST prototype, while the other group of five will receive a 2D VAST version on a tablet. Sessions will be held twice a week with each lasting approximately 30 minutes (i.e. 30 minutes +/- 5 minutes).

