Three primary metrics and three secondary metrics will be examined during the pilot study: **Change in Percentage of Correctly Transcribed Words Using Automatic Speech Recognition (ASR), Change in Articulation Accuracy, Change in Mean Length of Utterance (MLU), Parent Perceptions of Communication Changes Resulting from Study Participation, Change in Type-Token Ratios, and Change in Response Rate to Treatment Stimuli.** The frequency and duration of sessions is

based on our extensive previous research and is intended to ensure a statistically relevant number of data points to measure the learning progress of the students.

Impact will be measured via the following:

Change in Percentage of Correctly Transcribed Words Using Automatic Speech Recognition will be used as a measure of speech intelligibility. Specifically, the closed-captioning ASR on the Google Meet teleconferencing platform will be used as pre- and post-test measures to assess whether an individual has changed their ability to accurately articulate the target words. A higher percentage of correctly transcribed words will indicate articulatory accuracy and will provide a calculation of speech development rate. Due to the COVID-19 pandemic, distance learning will likely be a supplementary or primary medium of service delivery for children on the autism spectrum. Therefore, rating intelligibility on teleconferencing platforms may serve as a functional measure that could reflect subjects' communicative aptitude within a new social environment (i.e. distance learning).

Change in Articulation Accuracy will be calculated by two speech-language pathologists (SLP) transcribing the subjects' spoken production of the target words. Both SLPs will calculate the change in % of correct phonemes in each attempted stimulus by determining the correct number of phonemes in each of the subject's production of the target words.

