While all efforts will be made to keep data confidential, there is a small chance that participation in research may cause a loss of privacy. There is also a small risk of data loss and misuse or breach of private information. No physical, social, cultural, financial, legal, or other risks to subjects are expected from this study.

The data will be kept for ten years beyond the life of the project before all the files are destroyed, to allow for future longitudinal studies. While the data are kept for these additional years, the same storage protocols described above will be followed.

For the different group, electronic images (e.g., pdf), spreadsheets, and database files

Statistical Design and Power

We have used the following formula to calculate power and size of an experiments where there are >2 means:

$$n = 2 \left(\sigma \frac{z_{1-\alpha/(2\tau)} + z_{1-\beta}}{\mu_A - \mu_B} \right)^2$$

$$1 - \beta = \Phi \left(z - z_{1-\alpha/(2\tau)} \right) + \Phi \left(-z - z_{1-\alpha/(2\tau)} \right) \quad , \quad z = \frac{\mu_A - \mu_B}{\sigma \sqrt{\frac{2}{n}}}$$

Assumptions:

Power, $1-\beta$: 0.08

Type I error rate, α : 0.05

$\mu_A = 1$

$\mu_B = 2$

$\sigma = 1$

$\tau = 1$

Source: Chow S, Shao J, Wang H. 2008. Sample Size Calculations in Clinical Research. 2nd Ed. Chapman & Hall/CRC Biostatistics Series. page 71.

MLU, SIS, and articulation rate between groups will be tested using an ANOVA with pairwise comparisons.

may be created from paper-based field notes as researchers code data into an electronic form and de-identify (anonymize) response records. Data will then be protected as mentioned above.

IRB Review / Ethics / Informed Consent

As participants are children, all additional protections for children involved as subjects in research will be observed. We do not expect the study to involve greater than minimal risk and will obtain IRB approval of adequate provisions for soliciting the assent of the children and the permission of their parents or guardians.

The study involves children with ASD. Informed written consent from parents/guardians of the child participants is required prior to beginning any part of the study. Parents/guardians will be present at all times during the testing and will be able to stop

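### Does naming SIS and articulation rate in the test sentence leave two of the three primary outcomes without a planned test?

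*Combined protocol and SAP*

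**What the plan says.** Aim 3 names three main metrics: words correctly transcribed by ASR, articulation accuracy, and MLU. Study procedures / research method and the Outcome Measures table make the same three primary, each as a change from pre-test to post-test.

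Study procedures describes how each is obtained. The ASR percentage "will be used as a measure of speech intelligibility". For articulation, "Both SLPs will calculate the change in % of correct phonemes in each attempted stimulus". MLU is morphemes divided by utterances in a language sample.

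The same section says that caregivers "will help measure the impact of two pieces of technology", the VR headset and the tablet, and introduces the outcomes with "Impact will be measured via the following". For the ASR outcome, the Outcome Measures table adds that pre/post differences are compared both between and within groups. It also says that MLU gain is compared. Neither entry names a test.

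The test is named once, in Statistical Design and Power: "MLU, SIS, and articulation rate between groups will be tested using an ANOVA with pairwise comparisons". SIS appears nowhere else. Articulation rate recurs once, in Intended Use of Data, alongside intelligibility and MLU.

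**The concern.** One sentence carries the whole test specification, and two of its three variable names do not appear among the outcomes. Taken at face value, the ASR and articulation accuracy primaries have no named test, while a test is promised for an undefined acronym and for a rate that has no unit or procedure.

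Traceability would be at stake. If a report gave a p-value for SIS or for articulation rate, a reader could not tie it by name to a prespecified primary outcome. If either term meant something outside the outcome list, the set of tested variables would differ from the set of declared primaries.

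**Working it through.** The plan gives no figure on this point to reproduce. The check is a comparison of names, followed by a count of the possible readings.

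**Step 1: names side by side.**

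| Where | Intelligibility | Articulation | Utterance length |
|---|---|---|---|
| Aim 3, Study procedures, Outcome Measures | ASR words transcribed | articulation accuracy | MLU |
| Statistical Design and Power | SIS | articulation rate | MLU |
| Intended Use of Data | intelligibility | articulation rate | MLU |

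Matched by name in the test sentence: 1 of 3. SIS occurs once. Articulation rate occurs twice. Articulation accuracy occurs four times (once in Aim 3, twice in Study procedures, once in the outcome table) and never in the two sections that use articulation rate. The placement of SIS in the first column is an inference.

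**Step 2: support for that placement.** Study procedures presents the ASR percentage as the intelligibility measure. Intended Use of Data gives three targets that line up with the three primaries. Study procedures also closes by saying that staff will analyse the rates of all the listed metrics, so the plan uses the word rate loosely and not only for a quantity per unit of time.

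**Step 3: whether the pairing matters.** With MLU fixed, two labels are left for two outcomes, which gives 2 × 1 = 2 pairings.

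| Pairing | SIS | Articulation rate | Variables tested |
|---|---|---|---|
| A | ASR | articulation accuracy | ASR, articulation accuracy, MLU |
| B | articulation accuracy | ASR | ASR, articulation accuracy, MLU |

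The tested set is the same under both, and so is the test. With two groups there are 2 × 1 / 2 = 1 pairwise comparisons per outcome, so the plan yields three between-group comparisons under A or B.

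**Step 4: sample size.** The formula in the same section uses means of 1 and 2 and a standard deviation of 1, attached to no named outcome. Relabelling the variables leaves it unchanged.

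**Step 5: readings that would matter.**
- Both labels could refer to the ASR outcome, leaving articulation accuracy untested. The sentence would then list one variable twice under two names, which is hard to credit.
- One label could be a further measure. The plan lists six outcomes in all. The three secondary ones are parent perceptions, type-token ratio and response rate, and none of them is an intelligibility score or an articulation measure. No procedure for a seventh appears.

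**The case for a change.** The best case for a change is that the plan never states the mapping. The reader must expand an acronym and then accept a percentage of correct phonemes as a rate. Study procedures also blurs the line by saying of the ASR outcome: "A higher percentage of correctly transcribed words will indicate articulatory accuracy and will provide a calculation of speech development rate". Articulation and rate wording is thus attached to the ASR measure too, so articulation rate does not point only to the phoneme measure. A small pilot that declares primary outcomes and promises a between-group test should name them consistently, and doing so would cost only a few words.

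Part of this stands. The names do not match, the mapping is inferred, and a result reported under either stray label would be harder to trace. But the blurred wording bears only on the choice between pairings A and B, and that choice changes nothing. Nor can it fairly be said that the two variables are never measured or that the sentence cannot be followed: both likely referents have procedures in Study procedures, and the outcome table already commits to comparing the ASR differences between groups.

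**Conclusion.** No change to the plan follows. The mismatch is real as a matter of wording: one primary in three is matched by name, and two labels have no procedure of their own. Under either pairing, its effect on the tested set, the choice of test, the number of comparisons and the sample-size formula is nil. An analyst with the outcome table in hand would run the between-group ANOVA on the three primary changes and report them under their table names.

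This rests on two assumptions: that SIS and articulation rate are the ASR and articulation accuracy outcomes in some order, which the documents suggest but do not state, and that the comparison is between the two groups described in Study procedures. If the sponsor meant either term as a separate measure, the gap would be one of substance; nothing in the outcome list or the procedures indicates that.
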